## **15. DATA HANDLING AND RECORD KEEPING**

### **15.1. Electronic Case Report Forms (eCRFs)**

An eCRF must be completed by the Investigator or authorized delegate for each patient enrolled in Phase I and for each patient screened (enrolled/screening failure) in Phase II.

It is the Investigator's or authorized delegate's responsibility to ensure completion and to review and authorize release of the eCRF for each enrolled Clinical Trial Patient. The signature on the eCRF serves to attest that the information contained in the eCRF is true, accurate and reliable. At all times, the Investigator has full responsibility for the accuracy, legibility, completeness, and timeliness of all data (e.g., clinical data, laboratory results) reported in the eCRF and in the related data clarification tools (e.g., Data Clarification, Discrepancy Notes, Queries).

Source documents provide evidence for the existence of the participant and substantiate the integrity of the data collected. Source documents are filed at the Investigational Site. Source documents would include, but are not limited to, hospital/clinic records, physicians' and nurses' notes, appointment books, original laboratory result reports, ECG, x-rays, signed informed consent forms (ICF).

### **15.2. Record Retention**

Any study records and documents, including signed ICFs, pertaining to the conduct of the study, must be retained by the Investigator for the period of time specified in the Clinical Trial Agreement, unless local regulations or institutional policies require a longer retention period.

Data Controller (Sponsor) may store patient's data up to the expiration of the term required for undertaking and maintaining any IP claims (which is not less than 25 years). Biological samples may be stored for up to 15 years after the end of the research study and then will be destroyed.

No records may be destroyed during the retention period without the written approval of the Sponsor. No records may be transferred to another location or party without written notification to the Sponsor.

### **15.3. Confidentiality of Clinical Trial or Study Documents**

All documents and information given to the Investigator by the Sponsor with respect to NMS-03592088 and study MKIA-088-001 are strictly confidential.

The Investigator agrees that he/she and the members of his/her team will use the information only in the framework of this Clinical Trial, for carrying out the Clinical Trial Protocol. This agreement is binding as long as the confidential information has not been disclosed to the public by the Sponsor.

The Investigator must not disclose any information of Clinical Trial Protocol as well as any information extracted from it to other parties without the prior written authorization of the Sponsor. The only exception is upon request of the representatives of the Competent Authorities; in the latter case, the Investigator commits himself to informing the Sponsor prior to disclosure of information to these authorities.

## 16. ETHICS

### 16.1. Institutional Review Board (IRB)/Independent Ethics Committee (IEC)

Clinical Study Protocol, Protocol Amendments, Informed Consent Forms, Investigator Brochure and other relevant documents (e.g., advertisements) must be submitted to IRB(s)/IEC(s) by the Investigator(s) and/or Sponsor/Delegate Party in accordance with local regulations reviewed and approved by the IRB(s)/IEC(s) before the study is initiated.

Any amendments to the protocol will require IRB/IEC approval before implementation of changes made to the study design, except for changes necessary to eliminate an immediate hazard to study participants. In that case, the Investigator must notify the IRB/IEC, the Sponsor or Delegated Party and Regulatory Authority, as applicable, as soon as possible after the implementation.

The Investigator will be responsible for the following:

- Providing written summaries of the status of the study to the IRB/IEC annually or more frequently in accordance with the requirements, policies, and procedures established by the IRB/IEC
- Notifying the IRB/IEC of SAEs or other significant safety findings as required by IRB/IEC procedures.

### 16.2. Ethical Conduct of the Trial

This study will be conducted in accordance with and with the following:

- The Clinical Trial Protocol.
- Ethical principles derived from international guidelines including the Declaration of Helsinki [80] and Council for International Organizations of Medical Sciences (CIOMS) International Ethical Guidelines.
- Applicable ICH Good Clinical Practice (GCP) Guidelines.
- Current and applicable laws and regulations.

The Investigator will be responsible for:

- Providing oversight of the conduct of the study at the site and adherence to requirements of 21 CFR [78], ICH E6 R2 guidelines [77], the IRB/IEC, European regulation 536/2014 for clinical studies [79], as applicable, and all other applicable local regulations.

#### 16.2.1. Serious Breaches

The EU Regulation No 536/2014 and the EMA Guideline for the notification of serious breaches contain a requirement for the notification of serious breaches. A serious breach is

defined as “A breach of GCP or the trial protocol which is likely to affect to a significant degree

- (a) the safety or physical or mental integrity of the subjects of the trial; or
- (b) the scientific value of the trial”.

In the event that a serious breach is suspected, the Sponsor must be contacted. The serious breach will be reviewed by the Sponsor and, if appropriate, the Sponsor or entity/person legally authorised by the Sponsor will report it to the relevant Competent Authorities within 7 days.

### **16.3. Informed Consent Process**

It is the responsibility of the Investigator (or a person designated by the Investigator when accepted by local regulations) to give each individual full and adequate explanation regarding the nature of the study (e.g., objectives, aims, methods and procedures of the study, anticipated benefits, possible risks and potential hazards involved). The Investigator or his/her delegate will answer all questions regarding the study.

Participants must be informed that their participation is voluntary and that they have the right to withdraw from the study at any time.

Participants will be required to sign before any trial-related procedure is undertaken, a statement of informed consent (ICF) that meets the requirements of ICH guidelines, 21 CFR 50 and Health Insurance Portability and Accountability Act (HIPAA) requirements, where applicable, local regulations, and the IRB/IEC or study center.

The medical record must include a statement that written informed consent was obtained before the participant was enrolled in the study and the date the written consent was obtained. The authorized person obtaining the informed consent must also sign the ICF.

Participants must be re-consented to the most current version of the ICF(s) during their participation in the study.

A copy of the signed ICF(s) must be provided to the participant.

### **16.4. Personal Data Protection**

Participants will be assigned a unique identifier by the Sponsor or designee. Any participant records or datasets that are transferred to the Sponsor or designee will contain the identifier only; participant names or any information which would make the participant identifiable will not be transferred.

The participant must be informed that his/her personal study-related data will be used by the Sponsor or designee in accordance with local data protection law. The level of disclosure must also be explained to the participant.

The participant must be informed that his/her medical records may be examined by Clinical Quality Assurance auditors or other authorized personnel appointed by the Sponsor or designee, by appropriate IRB/IEC members, and by inspectors from Regulatory Authorities.

## **17. SPONSOR DISCONTINUATION CRITERIA**

Nerviano Medical Sciences reserves the right to discontinue the trial prior to inclusion of the intended number of patients, but intends only to exercise this right for valid scientific or administrative reasons. After such a decision, the Investigator must contact all participating patients. As directed by Nerviano Medical Sciences or the Delegated Party, all study materials must be collected and all case report forms completed to the greatest extent possible.

## **18. DISSEMINATION AND PUBLICATION OF RESULTS**

Results of the study may be presented or published. The conditions regulating dissemination of the information derived from this clinical study are described in the Clinical Trial Agreement.

## APPENDICES

### Appendix 1. ECOG Performance Status

Grade	ECOG PERFORMANCE STATUS
0	Fully active, able to carry on all pre-disease performance without restriction
1	Restricted in physically strenuous activity but ambulatory and able to carry out work of a light or sedentary nature, e.g., light house work, office work
2	Ambulatory and capable of all selfcare but unable to carry out any work activities; up and about more than 50% of waking hours
3	Capable of only limited selfcare; confined to bed or chair more than 50% of waking hours
4	Completely disabled; cannot carry on any selfcare; totally confined to bed or chair
5	Dead

## Appendix 2. Response Criteria in AML

Appendix 2.1.: Reporting Criteria in AML according to ELN 2022

Appendix 2.2.: Reporting Criteria in AML according to ELN 2017

NMS-03592088  
Protocol for Study MKIA-088-001

MKIA-088-001\_P9  
Version 9\_28 February 2024

## Appendix 2.1. Response Criteria in AML according to ELN 2022

Response Criteria in AML (2022)	
Category	Definition
Response	
Complete Remission (CR) *,†,‡	BM blasts <5%; absence of circulating blasts; NO EMD; ANC $\geq 1.0 \times 10^9/L$ (1000/ $\mu L$ ); platelet count $\geq 100 \times 10^9/L$ (100 000/ $\mu L$ )
CR with partial hematologic recovery (CRh) *,†,‡	ANC $\geq 0.5 \times 10^9/L$ (500/ $\mu L$ ) and platelet count $\geq 50 \times 10^9/L$ (50 000/ $\mu L$ ) otherwise all other CR criteria met  Comment: If CRh used, CRi should only include patients not meeting the definition of CRh
CR with incomplete hematologic recovery (CRi) *,†,‡	All CR criteria except for residual neutropenia $< 1.0 \times 10^9/L$ (1000/ $\mu L$ ) or thrombocytopenia $< 100 \times 10^9/L$ (100 000/ $\mu L$ )
Morphologic leukemia-free state (MLFS)	BM blasts <5%; absence of circulating blasts; NO EMD; NO hematologic recovery required ‡
Partial remission (PR)	Decrease of BM blast percentage to 5 to 25%; and decrease of pretreatment BM blast by at least 50%; All hematologic criteria of CR;
No response	Patient evaluable for response but not meeting the criteria for CR, CRh, CRi, MLFS or PR
Non-evaluable for response	Non-evaluable for response will include patients lacking an adequate bone marrow response evaluation. This category will include patients with early death, withdrawal prior to response assessment, or a technically suboptimal bone marrow sample precluding assessment
Progressive Disease	
Relapse	
Relapsed disease (after CR, CRh or CRi)	Bone marrow blasts $\geq 5\%$ ; or reappearance of blasts in the blood in at least 2 peripheral blood samples at least one week apart; or development of extramedullary disease

BM, bone marrow; PB, peripheral blood; ANC, absolute neutrophil count; EMD, extramedullary disease; WBC, white blood cell.

\*To recognize the potential for continuing improvements in blood counts after myelosuppressive therapy, response definitions for patients with marrow blast clearance (< 5%) may be adjusted to reflect the best hematologic response achieved prior to commencement of the next treatment cycle. Aspirate reports that include MLFS, CRh, or CRi should note the potential for post-marrow blood counts to alter the final response designation. Patients should not have received G-CSF, nor platelet transfusions within 7 days prior to hematologic response determination.

†For patients with CR, CRh, or CRi, the presence of a low percentage of circulating blasts in the blood may represent a regenerating marrow and should not be interpreted as persistent disease. In such cases the blasts generally disappear within a week.

‡A response landmark for CR, CRh, or CRi should be stated, eg, after 2 cycles of intensive therapy; this landmark may be longer for nonintensive based treatment options, eg, 180 days.

§Marrow should not merely be “aplastic”; bone marrow spicules should be present; at least 200 cells should be enumerated in the aspirate or cellularity should be at least 10% in the biopsy

(Adapted from Döhner H et al., [Blood](#). 2022 Sep 22;140(12):1345-1377)

Nerviano Medical Sciences S.r.l. - Confidential

## Appendix 2.2. Response Criteria in AML according to ELN 2017

**Response Criteria in AML (2017)**

Category	Definition
Response	
Complete Remission (CR)	BM blasts <5%; NO circulating blasts and blasts with Auer rods; NO EMD; ANC $\geq 1.0 \times 10^9/L$ (1000/ $\mu L$ ); platelet count $\geq 100 \times 10^9/L$ (100 000/ $\mu L$ )
CR with incomplete hematologic recovery (CR i )	All CR criteria except for residual neutropenia (<1.0 $\times 10^9/L$ [1000/ $\mu L$ ]) or thrombocytopenia (<100 $\times 10^9/L$ [100 000/ $\mu L$ ])
Morphologic leukemia-free state (MLFS)	BM blasts <5%; NO blasts with Auer rods; NO EMD; NO hematologic recovery required *
Partial remission (PR)	Decrease of BM blast to 5-25%; and decrease of pretreatment BM blast by at least 50%; All hematologic criteria of CR;
Stable Disease	Absence of CR, CR i , MLFS, PR; and criteria for PD not met #
Progressive Disease	
Progressive disease (PD)	Evidence for an increase in BM blast percentage and/or increase of absolute blast counts in the blood §: 
 
>50% increase in BM blasts over baseline (a minimum 15% increase in cases with <30% blasts at baseline; or persistent BM blast >70% over at least 3 months; without at least a 100% improvement in ANC (>0.5 <math>\times 10^9/L</math> [500/<math>\mu L</math>], and/or platelet >50 <math>\times 10^9/L</math> [50 000/<math>\mu L</math>] nontransfused); OR
 
>50% increase in PB blasts (WBC <math>\times</math> % blasts) to >25 <math>\times 10^9/L</math> (>25 000/<math>\mu L</math>) (in the absence of differentiation syndrome); OR
 
New EMD
 

Relapse	
Hematologic Relapse (after CR, CR i )	BM blasts $\geq 5\%$ ; or reappearance of blasts in the blood; or development of EMD

BM, bone marrow; PB, peripheral blood; ANC, absolute neutrophil count; EMD, extramedullary disease; WBC, white blood cell.

\* BM should not be merely 'aplastic': at least 200 cells should be enumerated or cellularity should be at least 10%

# Period of stable disease should last at least 3 months;

§ In general, at least 2 cycles of a novel agent should be administered; the protocol requires blast increase in 2 consecutive marrow assessments at least 4 wk apart; the date of progression should then be defined as of the first observation date

(From Döhner H et al., [Blood](#), 2017 Jan 26;129(4):424-447)

Appendix 3. Response criteria in CMML  
(not applicable for Phase II)

**Proposed Criteria for measurement of treatment response in adult CMML patients**

Complete Response (CR): presence of ALL of the following improvements *
BM: $\leq 5\%$ myeloblasts (including monocytic blast equivalent in case of CMML) with normal maturation of all cell lines and return to normal cellularity *
Osteomyelofibrosis absent or equal to "mild reticulin fibrosis" ( $\leq$ grade 1 fibrosis) #
Peripheral blood: WBC $\leq 10 \times 10^9$ cells/L Hgb $\geq 11$ g/dL Platelets $\geq 100 \times 10^9$ /L; $\leq 450 \times 10^9$ /L Neutrophils $\geq 1.0 \times 10^9$ /L Blasts 0% Neutrophil precursors reduced to $\leq 2\%$ Monocytes $\leq 1 \times 10^9$ /L Extramedullary disease: Complete resolution of extramedullary disease present before therapy (eg, cutaneous disease, disease-related serous effusions), including palpable hepatosplenomegaly
Complete Cytogenetic remission
Resolution of previously present chromosomal abnormality (known to be associated with myelodysplastic, syndrome myeloproliferative neoplasms, or MDS/MPN), as seen on classic karyotyping with minimal of 20 metaphases or FISH ^
Partial Remission
Normalization of peripheral counts and hepatosplenomegaly with bone marrow blasts (and blast equivalents) reduced by 50%, but remaining $>5\%$ of cellularity except in cases of MDS/MPN with $\leq 5\%$ bone marrow blasts at baseline
Marrow Response
Optimal marrow response: Presence of all marrow criteria necessary for CR without normalization of peripheral blood indices as presented above.
Partial marrow response: Bone marrow blasts (and blast equivalents) reduced by 50%, but remaining $>5\%$ of cellularity, or reduction in grading of reticulin fibrosis from baseline on at least 2 bone marrow evaluations spaced at least 2 mo apart

**Proposed Criteria for measurement of treatment response in adult CMML patients**

Clinical Benefit
Requires one of the following in the absence of progression or CR/partial response and independent of marrow response (clinical benefit response must be verified at $\geq 8$ wk) to be considered a clinical benefit
Erythroid response: Hgb increase by $\geq 2.0$ g/dL Transfusal independence (TI) for $\geq 8$ wk for patients requiring at least 4 packed red blood cell transfusions in the previous 8 wk Only red blood cell transfusions given based on physician's judgment for a pretreatment Hgb of $\leq 8.5$ g/dL will count in the red blood cell TI response evaluation §
Platelet response: Transfusion independence when previously requiring platelet transfusions of at least a rate of 4 platelet transfusions in the previous 8 wk Pretreatment $\leq 20 \times 10^9/L$ : increase from $<20 \times 10^9/L$ to $>20 \times 10^9/L$ and by at least 100% Pretreatment $>20 \times 10^9/L$ but $\leq 100 \times 10^9/L$ : absolute increase of $\geq 30 \times 10^9/L$ §
Neutrophil response Pretreatment $\leq 0.5 \times 10^9/L$ at least 100% increase and an absolute increase $\geq 0.5 \times 10^9/L$ Pretreatment $>0.5 \times 10^9/L$ and $\leq 1.0 \times 10^9/L$ At least 50% increase and an absolute increase $\geq 0.5 \times 10^9/L$ §
Spleen response Either a minimum 50% reduction in palpable splenomegaly of a spleen that is at least 10 cm at baseline or a spleen that is palpable at more than 5 cm at baseline becomes not palpable

Hgb, Hemoglobin.

\* Presence of dysplastic changes, which may be interpreted within the scope of normal range of dysplastic changes, may still exist in the presence of CR as allowed in MDS IWG. Marrow should exhibit age-adjusted normocellularity in CR. Persistent low-level dysplasia is permitted given patientivity of assignment of dysplasia.

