### 4.2.2. Secondary Endpoints (Phase I and Phase II)

- Overall safety profile of NMS-03592088 characterized by type, frequency, severity (graded using the National Cancer Institute Common Terminology Criteria for Adverse Events [NCI CTCAE] Version 5.0), timing and relationship to study therapy of adverse events, and laboratory and ECG abnormalities;
- Plasma pharmacokinetic profile and corresponding parameters of NMS-03592088 and its metabolites NMS-03593860 and NMS-03603422;
- Renal clearance and fraction of NMS-03592088 and its metabolites NMS-03593860 and NMS-03603422 excreted in urine (only Phase I);
- Secondary efficacy endpoints include: Best Response by category, Overall Survival (OS), Time to Response (TTR), Duration of Response (DoR), Event-Free Survival (EFS) and Relapse-free Survival (RFS) as defined by the ELN recommendations [6, 7] and disease specific International Working Group criteria [56] and proportion of patients bridged to hemopoietic stem cell transplantation (HSCT). For AML and in Phase II only: Complete Remission (CR) Rate, Complete Remission and Complete Remission with Partial Hematologic Recovery (CR/CRh) Rate, (CR/CRh/CRi) rate and Overall Response Rate (ORR: CRc + CRh + MLFS + PR) as defined by the 2022 ELN recommendations [6]. Rate of conversion from transfusion-dependence to transfusion independence.

CCI

█ [REDACTED]

█ [REDACTED]

█ [REDACTED]

█ [REDACTED]

█ [REDACTED]

█ [REDACTED]

█ [REDACTED]

NMS-03592088  
Protocol for Study MKIA-088-001

MKIA-088-001\_P9  
Version 9\_28 February 2024

CCI

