### 9.2.10.3. Hematopoietic Support

In Phase I prophylactic use of G-CSF or initiation of erythropoietin in Cycle 1 is not recommended, but may be instituted in Cycle  $\geq 2$  in patients who are having difficulty with severe neutropenia or anemia.

Patients who have been treated for  $\geq 4$  weeks with erythropoietin prior to the first cycle may continue on the existing treatment.

Patients with neutropenic fever or infection should be hospitalized promptly for IV antibiotic therapy and may receive therapeutic CSFs as appropriate.

Red blood cell and platelet transfusions should be administered as warranted.

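### In Phase I, CMML erythroid and neutrophil responses can be met through sustained erythropoietin or repeated G-CSF, because Appendix 3 sets no growth-factor condition

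*Protocol*

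**What the plan says.** **Supportive care (Protocol 9.2.10.3).** "In Phase I prophylactic use of G-CSF or initiation of erythropoietin in Cycle 1 is not recommended, but may be instituted in Cycle" 2 or later, "in patients who are having difficulty with severe neutropenia or anemia". Patients treated for at least 4 "weeks with erythropoietin prior to the first cycle may continue on the existing treatment". Those with neutropenic fever or infection "may receive therapeutic CSFs as appropriate", with no cycle limit stated.

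**CMML scoring (Protocol Appendix 3, Clinical Benefit).** A patient needs one "of the following in the absence of progression or CR/partial response and independent of marrow response", verified at 8 weeks or later. The relevant lines are:
- Erythroid: hemoglobin up by at least 2.0 g/dL, or at least 8 weeks of transfusion independence in patients who needed at least 4 packed red-cell transfusions in the previous 8 weeks. The only qualifier concerns which transfusions count: "Only red blood cell transfusions given based on physician's judgment for a pretreatment Hgb of" 8.5 g/dL or less.
- Neutrophil: an absolute rise of at least 0.5 x 10^9/L, together with at least a doubling (pretreatment count up to 0.5) or at least a 50% rise (pretreatment count above 0.5 and up to 1.0).

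Footnote § requires persistence on at least 2 analyses over at least 8 weeks and rules out transfusion support for maintained hemoglobin and platelets.

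**AML scoring (Protocol Appendix 2.1, footnote \*).** "Patients should not have received G-CSF, nor platelet transfusions within 7 days prior to hematologic response determination".

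**Endpoint.** Best response by category is a secondary endpoint (Protocol 4.2.2, SAP 3.2.2). Appendix 3 is marked as not applicable to Phase II.

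**The concern.** Erythropoietin is given to raise hemoglobin and G-CSF to raise neutrophils. Those are the quantities on which two of the CMML clinical-benefit responses are scored. If a patient receives either agent on study and the count rises, the criterion cannot separate its effect from that of the study drug.

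The error has a direction. Section 9.2.10.3 directs these agents to patients with low counts, and low-count patients are the ones with room to score a rise, so misclassification runs toward apparent activity. Phase I is uncontrolled, so no comparator group absorbs the effect, and one of its secondary objectives is to look for preliminary evidence of efficacy.

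**Working it through.** The documents give no figure on this point, so the check sets the texts side by side.

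1. **Erythropoietin started on study.** Section 9.2.10.3 allows the start from Cycle 2. A cycle is 28 days, or 4 weeks, so the 8-week verification spans 8 / 4 = 2 cycles. Take a patient whose hemoglobin is at least 2.0 g/dL above baseline and still is 8 weeks later, with erythropoietin continuing throughout. Every readable condition for erythroid response is met. The same holds for a patient who stays free of red-cell transfusion for those 8 weeks on erythropoietin.

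2. **Erythropoietin from before the study.** Stable treatment is already reflected in baseline hemoglobin, so a later rise is not obviously its effect. A dose increase after baseline is different. Section 9.2.10.3 speaks of continuing existing treatment and does not address an increase, and Appendix 3 has no rule for scoring one.

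3. **G-CSF.** A short course, for example for one febrile episode, would have to sustain the count on 2 analyses over 8 weeks and is largely screened out. Repeated courses that cover both analyses are not, and nothing in the neutrophil line prevents this.

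4. **Footnote §.** The symbol is attached to the erythroid, platelet and neutrophil lines, and its last sentence does refer to the absence of cytokine treatment. The subject of that sentence is a reduction in myeloid precursors and nucleated red cells, and monocytosis. It does not reach a hemoglobin or neutrophil rise. The one support exclusion that does concern hemoglobin names transfusions only.

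5. **Comparison with AML.** Appendix 2.1 applies a 7-day G-CSF exclusion to hematologic response. The same protocol has no counterpart for CMML.

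6. **SAP.** Section 9.4 summarises concomitant medications. Section 9.5 bars other anticancer treatment, including biological response modifiers, and does not address supportive growth factors. Neither sets a rule for scoring response.

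7. **Size.** An estimate needs the number of CMML patients, the proportion given each agent and the proportion of those who then meet a criterion. None is readable, so no percentage can be defended.

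**The case against.** The strongest reply is that little depends on this. Appendix 3 does not apply to Phase II. Clinical benefit is scored only in the absence of CR or partial response, so it cannot inflate either. RP2D selection rests on PK, anti-blast activity, biomarkers and safety among other features (Protocol 5.4), and the futility rule counts CR and CRi (Protocol Section 1, Statistical Methods). Expansion and backfill may be restricted to FLT3-positive AML. All of this stands and sets the grade.

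A second reply is that a scoring rule may sit elsewhere. Protocol 12.3.4 and the SAP efficacy section are blacked out, the appendix of mock-ups and algorithms is a separate document, and Section 11.3.4 points to the published IWG criteria with Appendix 3 as reference. This stands in part. It means that growth-factor effects can be scored as response, not that they are. Appendix 3 itself is readable and has no such rule.

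A third reply is that footnote § already covers cytokines. Its last sentence has no main verb, so a wider intention is possible, but the text has to say so.

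A reader might also carry the point into Phase II, to the "Rate of conversion from transfusion-dependence to transfusion independence". The documents do not support that. The permission to start erythropoietin is worded for Phase I, and the definition of that endpoint is not readable. Nor is a defect shown for CMML complete response, which requires marrow, fibrosis, monocyte and extramedullary criteria as well as counts.

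**Conclusion.** The point holds as a minor one. Applied as written, Appendix 3 lets sustained erythropoietin started or increased on study, or repeated G-CSF, produce a CMML clinical-benefit response in Phase I. The 8-week requirement narrows the gap without closing it, and the protocol already guards against the G-CSF part for AML.

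The effect is confined to best response by category in CMML patients, a descriptive secondary endpoint. The Phase II primary endpoint, CRc in AML, is untouched. The conclusion assumes that no unreadable text or separate appendix supplies a growth-factor rule; if one does, Appendix 3 only needs to cite it.

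**What to change.** Add to Appendix 3 and to the SAP:
- A CMML neutrophil response counts only if no G-CSF was given in the 7 days before each qualifying assessment, the window used in Appendix 2.1.
- A CMML erythroid response, by hemoglobin rise or by red-cell transfusion independence, counts only if erythropoietin was not started or increased since baseline. Stable pre-study erythropoietin does not disqualify.
- Responses are also reported with growth-factor use flagged.

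Protocol 9.2.10 already requires all concomitant medications in the eCRF, so the rule can be derived from recorded data, including for CMML patients already treated. The cost is about two sentences and one derivation step, and a few patients may lose a clinical-benefit label. This is a scoring rule only and leaves permitted supportive care as it is.
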